#### (2) Application of cardiac and carotid ultrasound probe

Probe models: S5-1, M5Sc, X5-1, 4D, PLI-2004BX; instrument models: Philips EPIQ7C, GE vivid E95 and Canon-Toshiba Ultrasound. The image display, storage and measurement modes will be uniformly preset by Philips, GE and Canon-Toshiba 's professional clinical doctors.

#### (3) Echocardiographic and carotid examination process

1) Use the standardized section specified in the ASE/EACVI guidelines to perform routine echocardiography and save the image (in DICOM format);

2) Connect ECG and record dynamic images (frame rate>40fps) of at least 5 cardiac cycles to ensure clear images (endocardium) and complete images (including epicardium); adjust the frame rate to 40% of the subject's heart rate;

3) M-mode images: M-mode images were recorded at the level of the chordae tendineae of the parasternal left ventricle in the long axis section, and the systolic displacement of the tricuspid annulus plane at the lateral wall of the tricuspid annulus was recorded at the apical four chamber section (TAPSE);

4) Two dimensional images: dynamic images were recorded and stored on the parasternal left ventricular long axis section, the parasternal left ventricular short axis section (mitral annulus level, papillary muscle level, apex level), the apical two chamber section, the apical three chamber section, the apical four chamber section, and the focused right ventricular four chamber section respectively;

5) Pulse Doppler image: mitral diastolic blood flow spectrum, tricuspid diastolic blood flow spectrum, aortic systolic blood flow spectrum and pulmonary systolic blood flow spectrum were recorded respectively;

6) Tissue Doppler images: TDI dynamic images were recorded in apical four chamber view; Pulsed tissue doppler images of mitral annular septum/lateral wall and tricuspid lateral wall were recorded on apical four chamber view;

7) 3D image: full volume imaging mode of Philips system: use the transthoracic realtime 3D probe X5-1 to collect images to ensure good connection of ECG signals. The four-chamber view of the left ventricular chamber fully displayed/the four-chamber view of the left atrium gathered/the four-chamber view of the right ventricle focused can be obtained on the apical view. Adjust the frame rate to more than 30 frames/second. Touch the Full Volume and rotate the 3D Opt key to the 4Beat position, Instruct the patient to hold his breath at the end of breath, press the Acquire button on the operation panel, and obtain the full volume information of the left ventricle (if EpiQ7c used, the Heart Model image will be retained after obtaining the ideal section). Four dimensional imaging mode of GE system: after entering the 4D mode, ensure that the ECG signal is well connected, obtain four-chamber view images that fully display the left ventricular cavity/four-chamber view images that focus on the right ventricle on the apical view, adjust the number of cardiac cycles (4-6 cardiac cycles), make the image frame rate meet the requirements (the image frame rate is required to be more than 40% of the subject's heart rate), instruct the patient to hold his breath after deep breath, Stabilize the probe and view the "splicing" artifacts in the volume reconstruction and front plane in the lower left window of the screen, or use Multi-Slice to evaluate the suture quality. If no artifacts are seen in several cardiac cycles, press Freeze. You can collect multiple cardiac cycles and then use the Cycle select control to select the best cycle. Press Img. on the operation panel Store saves the collected images.

8) Carotid image: adjust the position of probe to adjust with the targeted vessel straightly, and start the VFM program to collect the original data. After the images are collected, the data are further analyzed and processed using the online software of the machine. Trace the blood flow and the vascular wall at the junction of the vascular wall on the frame image of the cardiac cycle which the blood flow was fullest, and then run the software to automatically track the trace points and calculate the shear force at the corresponding position. To check the range shown at the edge of the screen and the automatic calculation results, and calibrate the calculation deviation caused by aliasing frame. Then the shear stress values of each cardiac cycle of this segment of blood vessel can be obtained.

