## (3) Group analysis:

1) For the healthy volunteers and hypertensive patients enrolled in the group: between 9:00

a.m. and 17:00 p.m. on the day of enrollment, at an interval of more than 4 hours, the patients performed two echocardiographic examinations in a calm state, measured and recorded their blood pressure at the same time (three measurements at an interval of 1-2 minutes), and measured the indicators at the two baseline levels on the day of enrollment. The changes of left ventricular global longitudial strain (GLS) and myocardial work (MW) in hypertension and healthy volunteer were compared, and the correlation between them and the changes of blood pressure was analyzed;

2) Analysis for hypertensive patients with different left ventricular configurations: configuration analysis was conducted based on the left ventricular remodeling standards recommended by ASE/EACVI 2015 guidelines and the EMINCA study combined with Ganau classification. Hypertensive patients were divided into normal left ventricular configuration group, left ventricular remodeling group, left ventricular eccentric hypertrophy group and left ventricular concentric hypertrophy group. Baseline, 12months, 24months, 36months and 48months echocardiography images were recorded and analyzed, compared the cardiac structure and functional indicators, and recorded clinical adverse events;

(2) Analysis for hypertensive patients with different left atrial configurations: according to the abnormal threshold of left atrial enlargement recommended by ASE/EACVI 2015 guidelines and the standard of Chinese left atrial enlargement recommended by EMNICA study, hypertensive patients were divided into normal left atrial group and left atrial enlargement group. Baseline, 12months, 24months, 36months and 48months echocardiography images were recorded and analyzed, compared the cardiac structure and functional indicators, and recorded clinical adverse events.

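### The general rule for dynamic images requires more than 40 fps and then sets the frame rate to 40% of heart rate; the two clauses conflict at every heart rate up to and including 100 bpm.

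*Protocol*

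**What the plan says.** The frame-rate rules are in the Protocol, under the standard operation procedure of echocardiography and carotid ultrasound, section (3), examination process.

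- **Step 2, dynamic images in general.** With the ECG connected, operators are to "record dynamic images (frame rate>40fps) of at least 5 cardiac cycles". The same numbered step ends with the instruction to "adjust the frame rate to 40% of the subject's heart rate". It gives no order of precedence, no unit conversion and no separate imaging mode for either clause.
- **Step 4, two-dimensional images.** It lists the views to record and gives no frame rate of its own, so step 2 is the only rule for these loops.
- **Step 7, 3D images.** For the Philips system: "Adjust the frame rate to more than 30 frames/second". For the GE system: "the image frame rate is required to be more than 40% of the subject's heart rate". Both are worded as minimums.

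The measurement sections on two-dimensional speckle tracking and on myocardial work draw on the dynamic loops. Under Group analysis, changes in global longitudinal strain (GLS) and myocardial work between two same-day examinations are compared between patients and volunteers, and cardiac function indices are compared between remodeling groups over follow-up.

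**The concern.** The first clause of step 2 is a floor. The second, as written, is a target, and at ordinary resting heart rates the target lies at or below the floor. An operator at rest-level heart rates cannot obey both and has to choose.

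The study plans 20 centres and equipment from three manufacturers. If some centres follow the floor and others the percentage, the loops behind strain and myocardial work will differ in temporal resolution from centre to centre. That would be avoidable between-centre variation in the functional comparisons, and some loops could break the Protocol's own floor while following its next clause.

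**Working it through.** **Inputs**

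- Floor: more than 40 fps, strict (step 2).
- Setting: 40% of heart rate, read as 0.40 × bpm in frames per second (step 2). The Protocol does not state the unit. This reading puts the clause on the same scale as the floor.
- Heart rate: not stated. Group analysis says that "the patients performed two echocardiographic examinations in a calm state", which supports a resting range. I assume 60 to 100 bpm.

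The Protocol derives no figure here, so there is nothing to reproduce first.

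**Step A: frame rate under the percentage clause.** Formula: fps = 0.40 × HR.

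**Step B: where the clauses become compatible.** 0.40 × HR > 40 requires HR > 40 / 0.40 = 100 bpm. At exactly 100 bpm the setting is 40 fps, which still fails a strict floor.

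**Step C: frames per beat.** Formula: fps × 60 / HR.

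- Percentage clause: 0.40 × HR × 60 / HR = 24 at any heart rate.
- Floor: above 40 × 60 / HR = 2400 / HR.

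| HR (bpm) | 0.40 × HR (fps) | Above 40 fps? | Frames per beat, 40% clause | Frames per beat at 40 fps | Shortfall of the 40% clause |
|---|---|---|---|---|---|
| 60 | 24 | no | 24 | 40.0 | 1 − 24/40.0 = 40% |
| 70 | 28 | no | 24 | 34.3 | 1 − 24/34.3 = 30% |
| 80 | 32 | no | 24 | 30.0 | 1 − 24/30.0 = 20% |
| 90 | 36 | no | 24 | 26.7 | 1 − 24/26.7 = 10% |
| 100 | 40 | no (equal) | 24 | 24.0 | 0% |
| 110 | 44 | yes | 24 | 21.8 | none |

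Because the floor is strict, the shortfalls up to 90 bpm are lower limits.

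**Step D: the same clause read as a minimum.** If step 2 required more than 40% of heart rate, as the GE 3D rule does, both conditions could be met at any heart rate. The binding limit would be 40 fps up to 100 bpm and 0.40 × HR above that. The conflict therefore comes entirely from wording the percentage as a target.

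**The case against.** The strongest reply is that this is a slip of wording. The only other use of the 40% figure, in the GE part of step 7, is a minimum, and under that reading nothing conflicts. The English is uneven throughout, so a lost *more than* is plausible. I accept this as the likely cause, but it does not settle what step 2 tells a site to do. Step 7 gives a different limit for each vendor's 3D mode and does not amend step 2. Read as a minimum, the clause would also be redundant up to 100 bpm, so an operator told to adjust the rate could fairly take it as a target.

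A second reply is that the procedures limit the harm. Each centre has one or two fixed, trained examiners. Vendor staff preset the display, storage and measurement modes uniformly. The central laboratory measures all images and reviews poor ones. The same-day comparison uses within-subject changes, so a stable centre-level difference would largely fall on both examinations alike. Most of this stands: it makes drift between visits at one centre unlikely and softens the same-day comparison. It does not remove differences between centres. Frame rate is not named among the presets, step 2 has it adjusted for each subject, and the image review names no frame-rate criterion.

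A reader might infer more than the Protocol supports:

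- **That the rules can never both be met.** They can, above 100 bpm.
- **That strain or work results will be biased.** The frame counts describe settings. Nothing in the Protocol links them to bias or variance in GLS or myocardial work, or shows that centres have in fact diverged.
- **That the main result is at risk.** The primary endpoints are clinical events. The groups are formed from LVMI, RWT and LAVI, which come from diameters, wall thicknesses and volumes, and the Cox, ROC and NRI analyses use those classifications, not strain.
- **That step 2 is specifically a two-dimensional rule.** It covers dynamic images in general. It reaches the strain loops because step 4 sets no rate of its own.

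**Conclusion.** The point holds as an internal contradiction in an operative acquisition rule. As written, the two clauses of step 2 conflict at every heart rate up to and including 100 bpm. Over the assumed range of 60 to 100 bpm the percentage clause gives 24 to 40 fps against a floor of more than 40. At 70 bpm that is 24 frames per beat against more than 34, about 30% fewer.

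This rests on reading the percentage as frames per second and on an assumed resting range. The 100 bpm break-even depends only on the first of these. The possible consequence is confined to the uniformity of strain and myocardial-work data across centres, and its size cannot be derived from the Protocol. The correction is worth making because it is small and these loops have no other frame-rate rule.

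**What to change.** Reconcile step 2 to a single rule before sites acquire further images. Either of two wordings removes the conflict:

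1. Keep the requirement of more than 40 fps and delete the 40% clause.
2. Keep it and reword the second clause as a minimum: *and more than 40% of the heart rate*, in line with the GE 3D rule.

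The sponsor should confirm which was meant, since the Protocol does not say.

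For images already held, the central laboratory should compare the frame rate of received loops with the chosen rule as part of its existing image-quality review. This applies where the rate is recorded: the Protocol says only that each folder includes acquisition time and operator. Loops below the limit should be flagged and handled in a sensitivity analysis of the strain and work indices. Automatic exclusion is better avoided, because it could create missing data concentrated in particular centres.

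The cost is one line in the imaging procedure, a notice to sites and a small checking workload.

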#### Echocardiographic and carotid measurement parameters

#### (1) M-mode and two-dimensional ultrasonic parameters:

1) Left ventricular end-diastolic diameter (LVEDD), left ventricular end-systolic diameter, left ventricular long diameter at end-diastolic, left ventricular basal transverse diameter and left ventricular middle transverse diameter;

2) End-diastolic ventricular septal thickness (IVSTd), end-diastolic left ventricular posterior wall thickness (LVPWTd);

3) Left atrial antero-posterior diameter, left atrial long diameter, left atrial transverse diameter, left atrial area and left atrial volume at end-systolic (Simpson method);

4) The antero-posterior diameter of right ventricle, the transverse diameter of right ventricular basal segment, the transverse diameter of right ventricular middle segment and the long diameter of right ventricle at end-diastolic;

5) The parasternal, proximal and distal diameters of the right ventricular outflow tract;6) Right atrial long diameter, right atrial transverse diameter, right atrial area and right atrial volume at end-systolic (Simpson method);

7) The middle systolic aortic annulus diameter, the end-diastolic aortic sinus diameter, the end-diastolic aortic sinus tube junction diameter and the end-diastolic ascending aorta diameter;

8) Left ventricular end diastolic volume, end-systolic volume and ejection fraction were measured by Simpson method in apical four-chamber view;

9) TAPSE;

10) RVFAC;

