### Inclusion criteria for hypertension:

- (1) Age 30-75 years old;
- (2) No antihypertensive drugs were used and three blood pressure measurements were conducted on different days, with systolic blood pressure ≥ 140 mmHg (1 mmHg=0.133 kPa) and/or diastolic blood pressure ≥ 90 mmHg; or have a history of hypertension and are using antihypertensive drugs, even if the blood pressure is lower than 140/90 mmHg;
- (3) Left ventricular ejection fraction was normal (LVEF  $\geq 0.5$ ).
- (4) All patients agreed to participate in the experiment and signed the informed consent form.

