## **EFFICACY ASSESSMENT**

Primary study endpoints: emerging atrial fibrillation, transient ischemic attack (TIA) or stroke, unstable angina, myocardial infarction, heart failure, coronary revascularization, cardiovascular death; Secondary study endpoints: decreased cardiac function with preserved ejection fraction; new cardiac remodeling; aortic aneurysm or aortic dissection; ECG showed that QTc (QT interval corrected by heart rate) was more than 500ms or QTc was longer than the baseline level for more than 60ms, emerging torsade de pointes ventricular tachycardia and other serious arrhythmias; the relationship between the deviations of blood pressure within the same day and the difference of cardiac function indexes.

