#### (2) Accessory examination

- 1) ECG examination: use resting ECG to evaluate arrhythmia and ST-T changes, etc.
- 2) Laboratory tests:

Fasting for more than 6 hours, blood routine, urine routine, fasting blood glucose, alanine aminotransferase, aspartate aminotransferase, blood urea nitrogen, creatinine, plasma total cholesterol, triglyceride, low-density lipoprotein cholesterol, high-density lipid Protein cholesterol, high-sensitivity C-reactive protein, prothrombin time, serum troponin, NT-proBNP.

3) Transthoracic echocardiography:

Two-dimensional dynamic images of left ventricular parasternal long axis, apical fourchamber heart, apical two-chamber heart, apical long axis, left ventricular apex level, papillary muscle level, and mitral valve level short-axis view; measure left ventricular ejection fraction (LVEF); Pulse wave Doppler was used to obtain the diastolic mitral valve orifice blood flow spectrum, and tissue Doppler was used to obtain the mitral valve annulus motion spectrum, and E/e' was calculated; Using speckle tracking imaging (STI) ultrasound technology to measure global longitudinal strain (GLS)/strain rate, global circumferential strain, global radial strain, global area strain (3D-GAS), left ventricular torsion, left ventricular rotation/untwisting speed, systolic dissynchrony index (SDI) and right ventricular free wall systolic peak strain (RVFWS) and so on.

4) Carotid ultrasound examination: the patient was the occipital supine position, with slightly raised jaw, the face was turned to one side, and the sternocleidomastoid muscle was fully exposed. The probe scans from the posterior edge of the sternocleidomastoid muscle to display the long axis and short axis images of the common carotid artery, internal and external carotid arteries, and bifurcation. The intima-media thickness, internal diameter and blood flow velocity were measured at 1-2 cm before the

bifurcation of the common carotid artery.

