#### (4) Myocardial work parameters:

According to the patient's blood pressure, left ventricular outflow tract spectral Doppler image, apical four chamber heart, apical two chamber heart, and apical three chamber heart section dynamic images, the pressure strain loop (PSL) is obtained by offline analyzing and calculating with Echopac software. Then the global work index (GWI), global constructive work (GCW), global wasted work (GWW), global work efficiency (GWE) and other indicators are obtained.

(5) The left ventricular remodeling parameters required in this study are calculated from the above obtained ultrasound parameters as follows:

LVM=0.8×1.04×[(IVSTd+LVEDD+LVPWTd)-LVEDD]+0.6

RWT =(LVPWTd×2)/LVEDD

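### 2D left ventricular volumes and LVEF are defined from the four-chamber plane only, although the two-chamber plane is already stored: a cheap gain in accuracy for the structure and function comparisons

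*Protocol*

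**What the plan says.** In the Protocol, Echocardiographic and carotid measurement parameters, part (1), item 8 sets the 2D method: "Left ventricular end diastolic volume, end-systolic volume and ejection fraction were measured by Simpson method in apical four-chamber view". No second plane is named, and no other 2D method for these quantities appears.

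The second plane is available. The examination process (part (3), item 4) records "the apical two chamber section, the apical three chamber section, the apical four chamber section". The view also appears in the echocardiography list under Accessory examination. Personnel requirements has images stored in DICOM format and sent to a central laboratory for offline measurement. Myocardial work parameters already draws on "apical four chamber heart, apical two chamber heart, and apical three chamber heart section dynamic images".

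LVEF appears in two other roles. Inclusion criterion (3) requires that "Left ventricular ejection fraction was normal", with a threshold of 0.5, and names no method. Efficacy Assessment lists "decreased cardiac function with preserved ejection fraction" as a secondary endpoint, with neither a method nor a cut-off.

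Three-dimensional ultrasound parameters adds 3D left ventricular volumes and a 3D LVEF. The protocol does not say whether the 2D or the 3D value governs any use. The 3D acquisition steps cover the Philips and GE systems only, while the equipment list also includes Canon-Toshiba.

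**The concern.** The disc-summation method needs two perpendicular diameters at each level of the ventricle. With one plane, the second diameter has to be assumed equal to the first, so every cross-section is treated as a circle. Reading the same plane three times and averaging, as Personnel requirements provides, reduces reader noise but leaves this shape error in place.

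The study exists to compare ventricles of different shape: normal geometry, concentric remodeling, eccentric hypertrophy and concentric hypertrophy. Group analysis compares structure and function indicators across these groups. If departure from a circular section varies between patients, it adds noise to volumes. If it differs on average between geometry classes, part of a between-group volume difference comes from the method. The information that would reduce this is already on the stored images.

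**Working it through.** **The plan's own design figure.** Sample size is the only design calculation in the protocol. Two-sided α = 0.05 and event rates of 4.9% and 2.2% give 985 per group at 90% power, against the stated 986 (power at 986 = 0.900; the protocol does not state a power). LVEF does not enter this calculation, so the point leaves it unchanged.

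**Volumes.** Let *a* be the four-chamber diameter and *b* the two-chamber diameter at a given level.

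- One-plane volume is proportional to Σ*a*².
- Biplane volume is proportional to Σ*ab*.
- If *b/a* is the same at all levels, the one-plane error relative to biplane is 1/(*b/a*) − 1.

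The protocol gives no diameter ratios, so these are assumed:

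| *b/a* | one-plane volume error |
|---|---|
| 0.90 | 1/0.90 − 1 = +11.1% |
| 0.95 | +5.3% |
| 1.00 | 0 |
| 1.05 | −4.8% |
| 1.10 | −9.1% |

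A ratio common to all patients rescales every volume alike. A spurious group difference needs the ratio to differ between groups: 1.00 in one and 0.95 in another would create an apparent difference of 5.3%.

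**LVEF.** Let *r* = (*b/a* at end-systole) / (*b/a* at end-diastole). Substituting the volumes above gives

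EF(one plane) = 1 − (1 − EF(biplane)) / *r*.

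If *r* = 1 the error cancels, even when the sections are far from circular. With assumed changes in the ratio:

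| EF (biplane) | *r* = 0.90 | *r* = 0.95 | *r* = 1.00 | *r* = 1.05 | *r* = 1.10 |
|---|---|---|---|---|---|
| 0.50 | 0.444 | 0.474 | 0.500 | 0.524 | 0.545 |
| 0.60 | 0.556 | 0.579 | 0.600 | 0.619 | 0.636 |

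A 5% change therefore moves an LVEF of 0.50 by 2.4 to 2.6 points, enough to cross the entry threshold. At 0.60 the shift is about 2 points and does not cross it.

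**What depends on item 8.** The geometry groups use LVMI and RWT, which the protocol calculates from linear wall and cavity dimensions. The atrial groups use LAVI. The primary endpoint is a set of clinical events. None of these uses the item 8 volumes or LVEF. What remains is the comparison of structure and function indicators, plus the entry check and the preserved-EF endpoint if they take this LVEF.

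**The case against.** The strongest reply is that nothing here is contradictory: one-plane Simpson is a clearly stated method, if a less exact one. That stands, and it is why this is an improvement and not an error.

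Four further objections limit the point.

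- **Entry and endpoint.** A reader might infer that item 8 supplies the LVEF for the 0.5 entry rule and the preserved-EF endpoint. The protocol does not say so. Neither place names a method, the endpoint names no cut-off, and it is not stated whether the entry value is the site's or the central laboratory's. If it is the site's, changing the central reading alters no entry decision.
- **Patient counts.** A reader might go on to estimate how many of the 2,200 planned patients are misclassified at 0.5. The documents give no measurement SD, no between-plane correlation and no LVEF distribution. The 2,200 are also enrolled patients, already selected on measured LVEF, so an error rate for everyone screened does not apply to them. No count is offered here.
- **3D values.** 3D volumes and LVEF are also derived and need no circular assumption, so the ventricle is not assessed from one plane alone. This stands in part. Nothing says the 3D value replaces the 2D one, and acquisition steps are given for two of the three listed brands. Equally, the equipment list covers cardiac and carotid work together, so it does not show that the third brand is used for cardiac imaging.
- **Differential bias.** That the shape error differs between geometry classes is possible, but the documents do not show it. Group analysis also speaks only of structure and function indicators in general, without naming LV volumes or LVEF.

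**Conclusion.** The point holds as a cheap improvement of low severity. Item 8 fixes a one-plane method where a biplane one is available from images already stored. The dependence of volume on the diameter ratio is exact geometry when that ratio is constant along the ventricle. The size is an assumption: +11% to −9% for ratios of 0.90 to 1.10. LVEF bias is conditional on the ratio changing through the cardiac cycle, at about 2.5 points near 0.50 for an assumed 5% change. The likely cost is less precise secondary comparisons of LV volume and function, with a possible shape artefact between groups. An effect on entry or on the preserved-EF endpoint depends on which LVEF serves them, and that is not stated.

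**What to change.** Amend item 8 so that LV end-diastolic volume, end-systolic volume and LVEF are measured by the biplane Simpson method from the apical four- and two-chamber views. Keep the four-chamber value as a fallback, flagged in the data, when the two-chamber image is unreadable. Use the biplane value in the comparisons across geometry groups.

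In Inclusion criteria and Efficacy Assessment, name the LVEF that applies: 2D or 3D, and site or central reading.

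The cost is a few sentences and one more tracing (end-diastole and end-systole) per examination by the same readers. No new views, visits or patients are needed, and because the images are stored, baseline values can be re-read for analysis after enrolment. The downside is that some patients will carry a flagged one-plane value.
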